### 6.7.2 Medical History

Medical history events will be coded using the latest Medical Dictionary for Regulatory Activities (MedDRA) version in place at the time of analysis and documented in the Data Management Plan (DMP). The version used will be indicated in the data summaries and listings. If updates to later versions are required during the study, this will be reflected in the DMP and the outputs. The number and percentage of subjects with medical history events will be presented by system organ class (SOC), and preferred term (PT), where SOC and PT will be presented in decreasing frequency of the total number of subjects with medical history events. All events will be listed.

## 6.8 Prior and Concomitant Medications

Medications will be coded using the latest World Health Organization Drug dictionary (WHO Drug) version in place at the time of analysis and documented in the DMP. The version used will be indicated in the data summaries and listings. If updates to later versions are required during the study, this will be reflected in the DMP and the outputs.

Prior medications are defined as those that started and ended prior to the administration of study drug. Medications that are ongoing at the administration of study drug or started after the time of administration of study drug will be deemed to be concomitant medications. If medication dates are incomplete and it is not clear

whether the medication was concomitant, the medication will be assumed to be concomitant.

The number and percentage of subjects taking prior medications and the number and percentage of subjects taking concomitant medications will be summarized separately. The summaries will be presented by medication class and standardized medication name, where medication class and standardized medication name will be presented in decreasing frequency of the total number of subjects with medications. In summary tables, subjects taking multiple medications in the same medication class or having the same standardized medication recorded multiple times in the study will be counted only once for that specific medication class and standardized medication name.

Medication data will be listed and concomitant medications will be flagged.

### **6.8.1 Rescue Medication**

Any concomitant medications deemed to be rescue medication will be indicated as such on the concomitant medications eCRF page.

All rescue medications will be flagged on the listing of prior and concomitant medications for the enrolled set. An analysis of rescue medication taken up to and including the Day 28 assessment for each subject will be conducted on the SfAS to assess any differences between dose groups in the requirement for rescue medication during this time period.

The number and percentage of subjects recording at least one concomitant medication identified as a rescue medication up to and including their Day 28 assessment will be presented by dose group for the SfAS.

Time to receipt of first concomitant rescue medication will also be derived in hours for each subject recording concomitant rescue medication up to and including Day 28 as:

*(Start date and time of first concomitant rescue medication) – (Date and time of study drug administration).*

Descriptive statistics will be presented for the time to receipt of concomitant rescue medication by dose group. The summary will be presented for the subset of subjects in the SfAS who record concomitant rescue medication in the time up and including to their Day 28 assessment.

Following review of the summaries described above, further post-hoc analyses of rescue medication may be conducted if considered worthwhile and there are sufficient subjects receiving rescue medication. Any post-hoc analyses to be performed will be fully defined in a SAP Addendum prior to conducting the analyses. This may include analysis of rescue medications taken up to Week 12 as appropriate.

## **6.9 Administration of Study Drug and Exposure**

Details regarding date and time of study drug administration will be listed. The dose group the subject was randomized to and the dose group the subject received will also be included in this listing.

## **6.10 Efficacy Evaluation**

### **6.10.1 Primary Endpoint**

#### **6.10.1.1 Primary Variable**

The primary efficacy endpoint of the study will be determined by the death of adult scabies mites at each post-Baseline RCM assessment, with death defined as the degradation (homogenization of internal structures and/or external anatomic structures, and increased reflectance) of the adult mite observed by RCM.

A minimum of 2 and maximum of 4 live adult scabies mites, each within its own distinct lesion, will be identified at Baseline by RCM for each subject. Only those lesions confirmed by RCM to contain a live adult scabies mite at Baseline will be recorded on the eCRF. These identified lesions will then be further assessed by RCM at Hours 4, 8, 24, 48 and 72 and Days 7, 14 and 28 for changes in mite morphology, movement and peristalsis.

For the purposes of analysis of the primary variable, only the 2, 3 or 4 individual live adult mites identified at Baseline by RCM will be evaluated at post-Baseline time points. It is not expected that juvenile mites will mature into adults within a selected lesion being evaluated for the primary endpoint. If there is evidence to suggest that this has occurred, the data will be reviewed on a case by case basis to determine how this should be handled in the analysis.

#### **6.10.1.2 Primary Endpoints**

Four separate endpoints will be analyzed in order to assess death of adult scabies mites, all of which will be considered key primary efficacy endpoints. Analysis of the death of adult scabies mites will be performed using the individual scabies mite as the unit of analysis and also the subject as the unit of analysis.

The endpoints to be analyzed using the scabies mite as the unit of analysis will be:

- Mortality rate for adult scabies mites at each post-Baseline RCM time point. Mortality rate at each time point will be calculated as the proportion of the total number of dead adult scabies mites from among the total number of live adult scabies mites identified at Baseline.
- Time to death of adult scabies mites for those identified as live at Baseline. Time to death of each adult scabies mite will be calculated in hours as (Date and time of first RCM assessment where mite confirmed dead) – (Date and time of study drug administration), for mites with confirmed death during the study. For mites without confirmed death during the study, time to death will be calculated in hours as (Date and time of Day 28 RCM assessment) – (Date and time of study drug administration), i.e. worst case.

The endpoints to be analyzed using subject as the unit of analysis will be:

- Mean proportion of dead adult scabies mites per subject at each post-Baseline RCM time point. The proportion of dead adult scabies mites for each individual subject at each time point will be calculated as the number of dead adult scabies mites from among the live adult scabies mites identified at Baseline for that subject.

- Proportion of subjects with 100% dead adult scabies mites from among the live adult scabies mites identified at Baseline for that subject, at each post-Baseline RCM time point.

### 6.10.1.3 Mite Status Derivation, Imputation and Missing Data

The approach for identifying live versus dead mites for the above primary endpoints is described below.

At Baseline, live adult mites will be defined by the following responses to the RCM assessment and only those lesions satisfying both of these criteria will be recorded on the eCRF:

- The response to 'Describe the mite stages present in the lesion?' includes 'Adult mites';
- The response to 'Does the mite have intact morphology?' is 'Yes'.

As the identification of these lesions is a requirement for randomization into the study, no missing data is anticipated for the assessment of live mites at Baseline.

At post-Baseline RCM assessments, an adult mite will be considered to be dead if at least one of the following conditions are met, based on the responses from the RCM assessment of the respective selected lesion:

- The response to 'Does the mite have intact morphology' is 'No';
- The response to 'Describe the mite stages present in the lesion' does not include 'Adult mites';
- The response to 'Is the lesion still visible' is 'No'.

These conditions are hierarchical, such that if a lesion is no longer visible it will not be possible to identify the mite stages present or the morphology of any mites, therefore the mite will be considered dead. Similarly, if the response to 'Describe the mite stages present in the lesion' does not contain 'Adult mites' it will not be possible to confirm intact morphology, therefore the mite will be considered dead.

Due to the life cycle of the mite and the subjective nature of skin assessments, it is possible that responses from the post-Baseline RCM assessments suggest that a mite previously declared as dead could be declared as live at a future assessment. To allow for this, the following rules will be applied to the post-Baseline assessments. Regardless of these rules, the baseline assessments (i.e. of live mite) will not be changed.

1. Any response of 'Unsure' to 'Does the mite have intact morphology' will be considered as equivalent to a status of 'live'.
2. One assessment with a status of 'dead' is required in order to declare the mite dead for all subsequent visits, where the death of the mite will be assumed to have occurred at the first visit with a status of 'dead'.
  - a. Where rescue medication has been taken (identified on the concomitant medications page of the eCRF), any mite death occurring after the start date of rescue medication will be ignored and the mite will continue to be considered alive. If the mite has already died prior to or on the start date of rescue medication, it will be considered dead for all subsequent visits as stated here.

3. Should the RCM responses indicate a status of 'live' at an assessment occurring after an assessment with a status of 'dead', this will be assumed to be a new infection and thus ignored, i.e. the mite identified at Baseline will still be assumed to have died. This will therefore not impact the analysis of the primary efficacy endpoints.
4. Where data are missing for any of the responses required to determine the status of a mite and therefore the mite status cannot be established, the status of the mite will be assumed not to have changed from the previous non-missing assessment (i.e. the last observation will be carried forward). This includes where a subject withdraws early, in which case the last observation will be carried forward for all remaining visits. Where the last observation is carried forward, this will still be subject to the above rules 1 to 3.

These imputation methods will be applied to all missing adult mite assessments, regardless of the number of lesions for which data are missing for a subject at a timepoint. If data are missing at the subject level (i.e. the RCM assessment is not completed for any lesion at a timepoint for a subject), all mites being evaluated will have their status imputed and therefore no subjects will be missing in the primary analysis summaries presented at each post-Baseline visit.

It should be noted that the above rules may not be exhaustive. If any ambiguity remains in the status of the mite after applying these rules, subject data will be reviewed on a case-by-case basis prior to breaking the blind.

All analyses of the dead/alive response described in the SAP for the primary endpoints will use the values obtained after applying the strategies for any imputation where there is ambiguity or missing data. Similarly references to 'first/last time point where dead/alive' refer to the first/last occurrence once these imputations have been applied. Following review of these analyses, post hoc sensitivity analyses may be considered to assess the impact of these imputations, as described in [Section 6.10.1.6](#).

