### 6.2 Endpoints

#### 6.2.1 Primary Endpoints

The primary endpoints of the study are:

- Efficacy will be determined by death of the mites, defined as the degradation (loss of internal and/or external anatomic structures) of the adult mite observed by RCM. Mites will be assessed at Hours 4, 8, 24, 48 and 72 and Days 7, 14 and 28 in not less than two lesions nominated pre-treatment.
- Safety will be assessed by the incidence and severity of AEs, physical examinations, and measurement of vital signs up to and including Week 12, and laboratory safety parameters up to and including Day 28.

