#### **9.4.7 Parasitology Assessments of the Scabies Mite**

*In vivo* assessments will be conducted on a minimum of 2 and a maximum of 4 live adult scabies mites, each within a distinct lesion. These assessments will be conducted using the Vivascope 3000® RCM. Some RCM assessments will be paired with high magnification dermatoscope assessments:

- RCM and dermoscopy: Baseline, and Hour 72, and Days 7, 14 and 28.
- RCM alone: Screening, and Hours 4, 8, 24 and 48.

By RCM, live adult scabies mites are defined by an inhomogenous (i.e. with internal structures discernable) ovoid refractive body. Short legs may be visible and vital functions such as peristalsis or movement within the burrow may be observable. Dermoscopy may be used to identify the location of mites before assessment by RCM. The lesions selected for assessment should be delineated to facilitate follow up, for example directly on the skin or using appropriate methods to map their location.

Once the assessable mites have been identified, optical sections will be captured using the RCM. Videos may also be captured as appropriate. Photographs at a minimum 10x magnification should be captured at the specified time points with a dermatoscope. Following image acquisition, the RCM and/or dermatoscope should be appropriately decontaminated.

These data will be recorded in the CRF. The full procedure for RCM and dermatoscope handling and image acquisition is detailed in the SRM.

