## 15.6 Study Endpoints

### 15.6.1 Key Efficacy Endpoints

The primary efficacy endpoint of the study will be determined by the death of adult scabies mites, with death defined as the degradation (homogenization of internal structures and/or external anatomic structures, and increased reflectance) of the adult mite observed by RCM. Mites will be assessed at Hours 4, 8, 24, 48 and 72 and Days 7, 14 and 28 in not less than two lesions nominated pre-treatment. The average proportion (crude mortality rate) of dead adult scabies mites per subject will be calculated as the number of dead adult scabies mites from among the live adult scabies mites identified at Baseline for each individual subject calculated at each time point measured. The proportion of subjects with 100% dead adult scabies mites from among the live adult scabies mites identified at Baseline calculated at each time point measured will also be reported.

The following are examples of key efficacy endpoints defined at the individual mite level of analysis:

- The mortality rate for adult scabies mites from among those identified at Baseline, calculated at each time point measured.
- The time-to-death of adult scabies mites from among those identified at Baseline.

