#### **6.10.1.6 Sensitivity Analysis**

Per [Section 6.4](#), the primary analyses may be repeated on the FAS post hoc if deemed worthwhile to assess any impact to the conclusions made.

Further sensitivity analyses, for example using different missing data or imputation approaches, may be considered post-hoc. This may include a completers analysis, repeating selected primary endpoint analyses without imputation of mite status due to missing data. Sensitivity analyses may also be added to assess the impact of imputations due to rescue medication or apparent new infections.

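### SAP 6.10.1.3 counts a mite as dead when no adult is recorded or the lesion is not visible, although death is defined as degradation observed by RCM; deaths should be shown by basis and bounded both ways

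*SAP*

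**What the plan says.** Protocol 6.2.1 bases efficacy on mite death, "defined as the degradation (loss of internal and/or external anatomic structures) of the adult mite observed by RCM". Protocol 15.6.1 has "death defined as the degradation (homogenization of internal structures and/or external anatomic structures, and increased reflectance) of the adult mite observed by RCM", and SAP 6.10.1.1 uses the same terms: "homogenization of internal structures and/or external anatomic structures, and increased reflectance) of the adult mite observed by RCM". The wordings differ in detail, but all three require the degradation to be seen.

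SAP 6.10.1.3 turns this into a rule on eCRF answers: "an adult mite will be considered to be dead if at least one of the following conditions are met". The three conditions are that morphology is not intact, that the recorded stages do not include an adult, or that the lesion is no longer visible. For the last, the stated reason is that "if a lesion is no longer visible it will not be possible to identify the mite stages present or the morphology of any mites". For the second, the reason is likewise that intact morphology cannot be confirmed.

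Other rules in the same section bear on this:

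- One dead status is final for all later visits.
- A later live reading is treated as a new infection and ignored.
- 'Unsure' morphology counts as live.
- When a response is missing, "the status of the mite will be assumed not to have changed from the previous non-missing assessment".
- Deaths after the start of rescue medication are ignored.

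The resulting status feeds every analysis of the four primary endpoints in SAP 6.10.1.2.

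**The concern.** Two of the three routes to death do not need anyone to see a degraded mite. A live mite that the operator does not find, for whatever reason, enters the results as a drug effect. Because one dead status is final, a later sighting of an intact adult in that lesion cannot correct the error. Every arm receives moxidectin and there is no comparator, so the trial cannot estimate how often live mites are lost from view.

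None of the planned tables would show the problem. The adult-mite table in SAP 6.10.3.1 sets an absent mite or an invisible lesion to 'not intact', and the mite-stage table counts subjects rather than mites. SAP 6.15 declares imputation of missing data but not this widening of the endpoint. At stake is the meaning of the mortality counts on which a descriptive dose-finding study relies.

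**Working it through.** The plan states no figure for this rule, so there is nothing to reproduce. The check compares definitions and then uses arithmetic on assumed rates.

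**1. The three routes against the definition**

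- *Morphology not intact:* a mite was seen and was degraded. This meets the definition.
- *No adult recorded:* the lesion was imaged and no adult was found. This is a completed negative reading, but no degradation was seen.
- *Lesion not visible:* neither the stages nor the morphology could be read. This is non-observation.

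**2. Effect on mortality.** Let p be true mortality and L the share of live mites not found by a given visit. L is an assumption, as the documents give none; 10% to 30% is shown, the same at every dose. Scored mortality = p + (1 − p)L.

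| L | p = 0% | p = 20% | p = 80% | Contrast, 80% v 20% |
|---|---|---|---|---|
| 0% | 0% | 20% | 80% | 60 points |
| 10% | 10% | 28% | 82% | 54 points |
| 20% | 20% | 36% | 84% | 48 points |
| 30% | 30% | 44% | 86% | 42 points |

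For a subject with two mites, treated as independent, with p = L = 20%, the chance of being scored 100% dead is 0.36² = 13%, against a true 0.20² = 4%.

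**3. If loss differs by dose.** The scored contrast is 0.60 + 0.20 × L(high) − 0.80 × L(low). It shrinks unless loss at the high dose is more than four times loss at the low dose. With L(high) = 30% and L(low) = 5%, it is 0.60 + 0.06 − 0.04 = 62 points, slightly wider than the truth. The shrinkage is therefore conditional. The upward shift in each dose's mortality is not.

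**4. How L accumulates.** With a per-visit chance q that a live mite is not found, independent across visits (again an assumption), and a status that cannot be reversed, L by the k-th visit is 1 − (1 − q)^k. At q = 5%, L is 1 − 0.95⁵ = 22.6% by Hour 72 (fifth visit) and 1 − 0.95⁷ = 30.2% by Day 14 (seventh). By Day 14 it is 6.8% at q = 1% and 52.2% at q = 10%. Repeated loss of the same mites would give less accumulation.

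**5. The opposite rule is also biased.** Suppose only observed degradation counts, and a share S of killed mites disappear before degradation is seen. Scored mortality is then p(1 − S). At an assumed S = 30%, 80% and 20% read as 56% and 14%, and the contrast is again 42 points.

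**6. What two bounds would show.** As an invented example, take 12 mites of which 7 are seen degraded, 3 are not found and 2 are intact. The current rule gives 10/12 = 83.3%. Observed degradation only gives 7/12 = 58.3%. The gap is the part that rests on mites not found.

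**The case against.** The best defence is that the SAP separates different inputs. 'Unsure' is stated doubt and a blank is missing data, whereas no adult recorded and lesion not visible are completed answers. An adult that was in the lesion and is no longer there could be read as the extreme case of the lost structures in Protocol 6.2.1. Protocol 9.4.7 also has safeguards: "The lesions selected for assessment should be delineated to facilitate follow up, for example directly on the skin", and dermoscopy may locate mites before RCM. At late visits a vanished mite or a healed lesion may well be a true kill.

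Much of this stands. It rules out treating both routes as pure non-observation, and it rules out simply replacing the current rule with the strict one, as step 5 shows. It does not make an unseen mite an observed degradation. The wording in Protocol 15.6.1 and SAP 6.10.1.1, which asks for homogenization and increased reflectance, does not fit absence. The late-visit argument is also weaker at Hours 4 to 72, when a missed mite is a plausible alternative.

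A reader might infer that the SAP shuts out a sensitivity analysis here. It does not. Section 6.10.1.6 says "Sensitivity analyses may also be added to assess the impact of imputations due to rescue medication or apparent new infections" and also allows other missing-data or imputation approaches. These are optional and post hoc, however, and none names this rule. The RCM listings would let someone recover the bases by hand (36 to 72 mites for 18 subjects with 2 to 4 each), but that is not a planned result.

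**Conclusion.** The point holds as a departure of the derivation from the stated endpoint. It moves each dose's mortality towards efficacy whenever a live mite is not found, and it reaches all four primary endpoints. Its size is unknown: the figures of 54, 48 and 42 points for a true 60 rest on assumed losses of 10%, 20% and 30% that are unrelated to dose.

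Two stronger readings are not supported. A reader might infer that the rule necessarily blurs the ranking of doses; that depends on how loss varies with dose, which the documents do not say. A reader might also infer that the Protocol Steering Committee's advice on adding 36 mg rests on these figures. Protocol 13 and SAP 5.1 name mite mortality or time to death as guides, but neither says that the committee's figures used this derivation.

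The study is descriptive and makes no claim on power or type I error, so none is affected. The change is worth making because the counts themselves are the result.

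**What to change.** 1. In SAP 6.10.1.3, derive the basis of each death (degraded mite observed, adult not recorded, lesion not visible) and tabulate deaths by basis, dose and time point.
2. In SAP 6.10.1.6, pre-specify all four primary endpoints under two bounds, presented side by side. The upper bound is the current rule. The lower bound counts a death only when intact morphology is answered 'No'. Mites not found are carried forward under rule 4, so one already seen degraded stays dead.
3. In SAP 6.15, record that the operational rule is wider than the endpoint definition.

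The cost is SAP wording and one further set of tables from eCRF items already collected. The lower bound will understate mortality, and may also shrink dose contrasts, where killed mites are shed or lesions heal before degradation is seen, mainly at late visits. It should therefore be read as a bound and not as a replacement estimate.
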